Delivery of manuscript	01-05-2018

7. Rationale and background

Venous thromboembolism (VTE) in young women is rare, with an annual incidence of approximately 2-5 per 10 000 women (6). An increased risk of VTE associated with oral contraceptive use has long been established and while the absolute risk of VTE in young women is low, the fact that millions of women worldwide are using oral contraceptives indicates that these preparations are responsible for a large number of cases of VTE

(3, 7-11). Several large studies including a review in 2013 by the European Medicines Agency (EMA) concluded that the risk of VTE associated with hormonal contraceptive preparations which contained gestodene, desogestrel, or drospirenone was increased compared with hormonal contraceptive preparations containing levonorgestrel (1, 5, 12, 13).

After the publication of the review by the EMA, the European Commission adopted on 16 2014, a legally binding decision to update the product information of all combined hormonal contraceptives (CHC) throughout the European Union. This included information to patients: awareness of factors that increase the risk of VTE and information to health care professionals: the type of CHC with the lowest VTE risk (levonorgestrel, norethisterone, or norgestimate) and the fact that CHC are contraindicated in the presence of one serious or multiple risk factors for VTE. It is currently unknown whether the publication of this review led to a change in prescription patterns and a subsequent change in the incidence of VTE in young women.

The aim of this study is therefore to investigate the CHC utilisation and prescribing patterns in a sample of Three European Union Member states (Denmark, United Kingdom, and the Netherlands) in a time period including the completion of the 2013 review and implementation of the resulting recommendations and to estimate any changes in the incidence of VTE between the two periods specified.

This study will provide evidence regarding the necessity of the recommendation to use safer oral contraceptive preparations, as it will show whether the implementation of the recommendation was successful and whether it actually affected the incidence of VTE in the target population.

8. Research question and objectives

Was there a change in CHC prescribing patterns between the periods January 2012 – January 2014 and February 2014 – December 2015 and, if so, was there a subsequent change in the incidence rate of VTE?

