For each calendar year, we provide estimates of the number and proportion of new users of each oral contraceptive type and the number and proportion of switchers (from one type to another or to a different dose) overall and stratified by age at initiation of oral contraceptives (18-24, 25-29, 30-34, 35-39, 40-44 and 45-49 years) and socioeconomic status.

In order to assess the effects of the review on initiation as well as on switching of treatment (between January 2012- January 2014 and between February 2014- December 2015), we will perform segmented regression analysis (16).

For our analysis we will use SPSS for Windows, release 23.0.

WP2

Objectives

To obtain the number and proportion of women (within each calendar window) initiating different types of oral contraceptives or per switching pattern using data from the Danish Civil Registration System and the Danish National Prescription Registry.

Methods

Study population

For the Danish drug utilization study, we will obtain information on use of oral contraceptives from the Danish National Prescription Registry, demographic information (age, sex, vital status and migration) from the Danish Civil Registration System and data on income and education at Statistics Denmark in the study period (1 January 2012 to 31

December 2015). Women with no oral contraceptives prescription prior to study start date (from 2010 onwards) will be followed up until they receive their first oral contraceptive dispensation, become 50 years of age, 31 December 2015, or they emigrate or die. The new users are defined as women with no prior prescription of CHC in the two years before.

To investigate switching patterns among prevalent users, individuals will be defined as prevalent users if they had at least one dispensation for an oral contraceptive between 1 July 2011 and 1 August 2015. Prevalent users will be followed from the date of the study start/entry until switch of treatment (defined as prescription of a new type of CHC before expiration of the days supplied of the previous drug), becoming 50 years of age, December 31st 2015, death or emigration, whichever comes first.

Oral contraceptives

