We will consider each CHC individually and, additional to the analysis of individual types of combined oral contraceptives, in our analysis, we will group CHC together according to generation (i.e., the second generation containing levonorgestrel/norgestimate and ethinylestradiol, the third generation containing gestodene/desogestrel and ethinylestradiol and the newer generations containing drospirenone and ethinylestradiol).

Analysis

For each calendar year, we provide estimates of the proportion of each oral contraceptive type and the number of switchers (from one type to another or to a different pill strength) overall and stratified by age at initiation of CHC (18-24, 25-29, 30-34, 35-39, 40-44 and 45-49 years).

We will estimate incidence rates of initiating CHC use per 1000 person years at risk including 95% confidence intervals for each calendar year using incident dispensation as the indicator of CHC initiation. Similarly, we will provide estimates of incidence rates of switching per 1000 person years at risk including 95% confidence intervals for each calendar year of the study period.

In order to assess the effects of the review on initiation as well as on switching of treatment (between January 2012- January 2014 and between February 2014- December 2015), we will perform segmented regression analysis, taking the two time periods into account.

For our analyses we will be using SAS version 9.2 or higher.

WP3

Objectives

To obtain the number and proportion of women initiating different types of oral contraceptives in UK between January 2012 to December 2015 and to investigate switching pattern using data from The Health Improvement Network (THIN) primary care database.

Methods

Study population

For the UK drug utilization study, we will make use of anonymised primary care data from when women consult their general practice to obtain oral contraceptives. For each calendar year of the study period (1 January 2012 to 31 December 2015) we will identify women who were between 18 and 49 years and have been registered for at least two years prior with one of the general practices that contributed data to THIN. Individuals with no oral contraceptives prescription prior to study entry (from 2010 onwards) will be followed up until they receive their first oral contraceptive prescription, they become 50 years of age, 31 December 2015, or leave the practice. The new users are defined as women with no prior prescription of CHC in the two years before.

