To investigate switching patterns among prevalent users, individuals will be defined as prevalent users if they had at least one prescription of oral contraceptives between 1 July 2011 and 1 August 2015. Prevalent users will be followed until switch of treatment, six months after last prescription, becoming 50 years of age, December 31st 2015, leave the practice or death, whichever comes first.

Oral contraceptives

We will consider each CHC individually and, additional to the analysis of individual types of combined oral contraceptives, in our analysis, we will group CHC together according to generation (i.e., the second generation containing levonorgestrel/norgestimate and ethinylestradiol, the third generation containing gestodene/desogestrel and ethinylestradiol and the newer generations containing drospirenone and ethinylestradiol).

Analysis

For each calendar year, we provide estimates of the number of initiators of each oral contraceptive type and the number of switchers (from one type to another or to a different dose) overall and stratified by age at initiation of CHC (18-24, 25-29, 30-34, 35-39, 40-44 and 45-49 years), social deprivation (Quintiles of Townsend Deprivation scores), body mass index (BMI) and smoking status.

We will tabulate the estimates of new users by 1000 person years at risk including 95% confidence intervals for each calendar year. Similarly, we will provide estimates of switchers by 1000 person years at risk including 95% confidence intervals for each calendar year of the study period.

In order to assess the effects of the review on initiation as well as on switching of treatment (between January 2012- January 2014 and between February 2014- December 2015), we will perform segmented regression analysis.

For our analyses we will be using Stata version 14 or higher.

WP4

Objectives

To assess changes in the incidence rate of VTE among women using CHCs of reproductive age in the Netherlands between January 2012- January 2014 and February 2014- December 2015 and to investigate any measurable association between these changes and the observed changes in CHC use.

Methods

Study population

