From segmented regression analysis (WP3), we will obtain information on a potential change in the proportion of initiators of each generation of CHC between January 2012-January 2014 and February 2014- December 2015. Since we have information about the prescription patterns among new users, we can assess whether the changes observed in the proportions of each generation is associated with changes in the incidence rate of VTE in women initiating oral contraceptive use.

Furthermore, we can study the changes in the incidence of VTE within users of different types

(and generations) of oral contraceptives. A change in this incidence over time, may indicate that certain preparations are prescribed to low/high risk individuals.

Analysis will be performed using Stata version 14 or higher.

WP7

Outline for the study report

The study report will combine the findings from all 6 work packages. Data from three countries will be used to report on the trends in first ever user prescribing in the two years preceding the relevant Commission Decision January 2012 – January 2014 and the period following the decision February 2014 – December 2015 . Furthermore, using different research strategies, we will report on the changes in the incidences of VTE in the different observation windows, separately for each country. The report will provide evidence regarding the necessity of the recommendation to use safer oral contraceptive preparations as it will show whether the implementation of the recommendation was successful and whether it actually affected the incidence of VTE in the target population.

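### Among current users, stopping CHC is never an outcome, and under the WP2 follow-up rule it dilutes the Danish switching rate

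*Protocol*

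**What the plan says.** Section 7 reports two messages to prescribers in the Commission Decision. One names the CHC types with the lowest VTE risk. The other is that "CHC are contraindicated in the presence of one serious or multiple risk factors for VTE". Objective 3 (section 8) asks about utilisation changes in groups defined by the SmPC warnings and contraindications.

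The outcomes for current users, all in section 9.2, are these:

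- **WP1 (Netherlands):** "the number and proportion of switchers (from one type to another or to a different dose"). CHCs are the drugs considered, and no follow-up rule for switching is stated.
- **WP2 (Denmark):** follow-up runs to "switch of treatment (defined as prescription of a new type of CHC before expiration of the days supplied of the previous drug"), or "becoming 50 years of age, December 31st 2015, death or emigration, whichever comes first". The analysis paragraph counts "the number of switchers (from one type to another or to a different pill strength") and reports switching per 1000 person-years.
- **WP3 (UK):** "the number of switchers (from one type to another or to a different dose"), also per 1000 person-years. "Prevalent users will be followed until switch of treatment, six months after last prescription", age 50, end of 2015, leaving the practice or death.

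The Abstract's data analysis paragraph plans, for Denmark and the UK, to relate overall change in CHC use to overall change in VTE incidence, with age-standardised initiations as the measure of use. Of the report, WP7 says that "it will show whether the implementation of the recommendation was successful".

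**The concern.** For a current user in a contraindicated group, the response that the second message implies is leaving CHC. No work package counts that. A change of strength within the same product, which neither message addresses, does count. The plan's picture of overall CHC use is therefore built from starts and changes within the class, with no measure of exits.

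This matters in two ways. First, one of the two messages cannot be evaluated in the women already exposed when the decision was adopted. Second, if stopping became more common after February 2014, the Danish switching rate could fall for that reason alone and be read as a change in switching.

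**Working it through.** **1. The plan's only switching figure.** The Abstract's study size paragraph gives about 1.3 million Dutch users, 16% switching in two years and about 212 000 switches. 1 300 000 × 0.16 = 208 000, which is 1.9% below 212 000 and explained by rounding (212 000 / 0.16 = 1.325 million users). The figure reproduces. It counts only changes from one oral contraceptive agent to another and says nothing about stopping.

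**2. What happens to a woman who stops and does not restart.**

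| | Outcome? | Ends follow-up for switching? |
|---|---|---|
| WP1 | No | No rule stated |
| WP2 | No | No |
| WP3 | No | Yes, six months after the last prescription |

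In WP2 the event requires supply in hand, while the listed ends of follow-up do not include loss of supply. After supply expires she can have no event but stays in the denominator. In WP3 the extra time is at most six months. The same behaviour is handled differently in the two countries.

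**3. Size of the denominator effect in WP2 (illustration).** The switch hazard s comes from the protocol's 16%: s = −ln(0.84)/2 = 0.0872 per year. The stopping hazard d is assumed, because the protocol gives none. Hazards are constant, women who stop do not restart, supply left at stopping is ignored, and T = 2 years. Put h = s + d.

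- Time on CHC: A = (1 − e^(−hT))/h
- Time after stopping that WP2 still counts: B = d × [T/h − (1 − e^(−hT))/h²]
- Switches per woman: s × A
- Rate if follow-up ends at stopping: sA/A = s
- Rate under the WP2 rule: sA/(A + B)

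For d = 0.2: h = 0.2872, A = 1.521, B = 0.333, switches = 0.1326, and the WP2 rate is 0.1326/1.855 = 71.5 per 1000 person-years.

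| Assumed d per year | Stopped within 2 years, uncounted | Rate, follow-up ended at stopping | Rate, WP2 rule |
|---|---|---|---|
| 0 | 0% | 87.2 | 87.2 |
| 0.1 | 17% | 87.2 | 78.8 |
| 0.2 | 30% | 87.2 | 71.5 |
| 0.3 | 42% | 87.2 | 65.1 |
| 0.4 | 51% | 87.2 | 59.5 |

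If d rose from 0.1 in one window to 0.2 in the next, the rate would drop from 78.8 to 71.5, a ratio of 0.91, with switching behaviour unchanged. This treats each window as a fresh two-year cohort and applies a Dutch proportion to the Danish rule. It shows direction and rough scale, not a forecast.

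**4. Why exits matter for VTE.** From the risk table in the Abstract, moving from drospirenone, gestodene or desogestrel (9 to 12 per 10 000 per year) to the lowest-risk types (5 to 7) is a difference of 2 to 7. Leaving CHC (about 2) is a difference of 7 to 10. These are averages over users and need not hold for contraindicated women.

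**The case against.** The strongest reply is that the endpoint fits its objective. Objective 2 concerns switching between products, and a change within CHC is a natural reading of that. WP7 also describes the recommendation as one to use safer preparations, which new-user proportions by generation and switching between types measure directly. This stands. A reader might infer that the study cannot show whether implementation succeeded at all. The protocol does not support that reading.

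A reader might also infer that full compliance with the contraindication message would register as no change. That goes too far. The message also governs who starts CHC, and initiation is analysed by age in all three countries and by BMI and smoking in the UK. The gap is confined to current users.

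A third tempting inference is that switching falls because women at risk leave follow-up. In WP2 stopping does not end follow-up; the distortion comes from their staying in. In WP3 person-time ends along with them, so the rate is not lowered by that alone.

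Nor does the gap break the link sought in Objective 4, which rests mainly on initiators by generation. What remains is that WP5 follows women aged 18 to 49 whether or not they still use CHC. A fall in VTE from women leaving CHC would enter its rates with no utilisation measure to set against it.

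Two textual points deserve weight. WP2 speaks of person-years at risk, and an analyst might drop time without supply on that ground, but the stated end of follow-up does not say so. WP3 does not define a switch as CHC-only in so many words. The restriction is read from its list of drugs considered and its type-or-dose wording.

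**Conclusion.** The point holds in limited form. Among current users, WP1 to WP3 measure only changes within CHC, so the plan cannot show whether the contraindication message was implemented in them, and its account of overall change in CHC use leaves out women who exit. Choice of CHC type and initiation remain assessable.

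Separately, the WP2 rule pulls the Danish switching rate down as stopping rises: from 87.2 to between 78.8 and 59.5 per 1000 person-years over assumed stopping hazards of 0.1 to 0.4 per year. The direction follows from the stated rules, provided that person-time is counted as written. The size rests on the assumed hazards. The protocol gives no number of women leaving CHC, so the actual effect on any result is unknown. This should be corrected, but it does not undermine the study as a whole.

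**What to change.** 1. Add CHC discontinuation as an outcome for prevalent users in WP1 to WP3: no new CHC within one stated grace period after supply ends, the same in all three countries. Report it per 1000 person-years on CHC in the segmented regression already planned, by age everywhere and by BMI and smoking in the UK.
2. Where progestogen-only codes can be added to the extract, report change to a progestogen-only product separately.
3. In WP2 and WP3, count switching person-time only while CHC supply lasts plus the grace period.
4. Tabulate strength-only changes apart from changes of progestogen.
5. If item 1 is not done, state in WP7 that the conclusions cover initiation and choice among CHC products, not withdrawal of CHC from current users at risk.

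**Cost.** Items 1, 3 and 4 use CHC records already in the extract. Item 2 needs extra codes. Item 5 is a text edit.

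**Downside.** Women stop for other reasons, such as a planned pregnancy, so only the change in stopping at the break is interpretable. Contraindicated women cannot be isolated with the listed Dutch and Danish stratifiers, so results by risk group will be informative mainly in the UK.

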It is unknown whether the publication of the review has led to a change in prescribing patterns and a subsequent change in the incidence of VTE. Therefore, we want to investigate the CHC prescribing patterns among women in three European Union Member states (the Netherlands, Denmark and the United Kingdom) in a time period including the completion of the 2013 review and implementation of the resulting recommendations and to estimate any changes in the incidence of VTE between the two periods specified.

Risk of developing a blood clot (VTE) in a year	
Women not using a combined hormonal pill/patch/ring and are not pregnant	About 2 out of 10,000 women
Women using a CHC containing levonorgestrel, norethisterone or norgestimate	About 5-7 out of 10,000 women
Women using a CHC containing etonogestrel or norelgestromin	About 6-12 out of 10,000 women
Women using a CHC containing drospirenone, gestodene or desogestrel	About 9-12 out of 10,000 women
Women using a CHC containing chlormadinone, dienogest or nomegestrol	Not yet known ¹

¹ Further studies are ongoing or planned to collect sufficient data to estimate the risk for these products.

Research question

Was there a change in CHC prescribing patterns between the periods January 2012 – January 2014 and February 2014 – December 2015 and, if so, was there a subsequent change in the incidence rate of VTE?

Objectives

1. To investigate trends in new user (initiators) prescribing patterns in the two years preceding the relevant Commission Decision (January 2012 – January 2014) and in a similar period following the decision (February 2014 – December 2015).
2. To investigate switching patterns between products among prevalent users including reasons for changes (e.g., reimbursement or regulatory and clinical guidance).
3. Within Objectives 1 and 2, to examine any changes in utilisation in groups defined by patient's clinical and demographic risk factors for VTE as detailed in the warnings and contraindications in the European Union Summary of Product Characteristics (SmPC)(2).
4. To examine any differences in the incidence rates of VTE between the two periods

specified and, in light of the results for Objective 1-3, to investigate any measurable association between the observed changes in CHC use and changes in the VTE incidence rates.

Study design:

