9.2 Data collection and analysis

WP1

Objectives

To obtain the number and proportion of women (within each calendar window) initiating different types of oral contraceptives or per switching pattern using data from the SFK.

Methods

Study population

For the Dutch drug utilization study, we will make use of de-identified data obtained through The SFK, which gathers its data from >95% of community pharmacies in the Netherlands (<https://www.sfk.nl/english>). All women who had one or more prescription of CHC in the period from January 2012 through December 2015 will be included, i.e., both new users as well as prevalent users. Age at initiation and 4 digit postcodes is also available in the SFK database which allows further characterization of CHC users by age and socioeconomic status. The latter information will be retrieved by using information from the Central Bureau of Statistics (CBS), the Netherlands, which keeps record of socioeconomic status by use of 4-digit postcodes. Although SFK does not indicate if women had venous thrombotic disease for which they need to receive anticoagulant treatment, it can be approximated by the first dose of oral anticoagulant (direct oral anticoagulant (DOAC)) or duration of anticoagulant (vitamin K antagonist), which is specific for VTE.

Per calendar year of the study period (1 January 2012 to 31 December 2015), we will identify new users of CHC use. New users will be defined as women between the ages of 18 to 49 years old who do not have a prior prescription of CHC in the two years before.

Furthermore, we will obtain information on prevalent users of CHC and thereby we can assess all individual changes (switches) in CHC in the study period (1 January 2012 to 31 December 2015). Prevalent users of CHC are defined as women who used at least one cycle of oral contraceptives.

Oral contraceptives

We will consider CHCs. According to the EMA review, the CHCs which contain levonorgestrel, norgestimate and norethisterone show the lowest risk of VTE (1). Therefore, additional to the analysis of individual types of combined oral contraceptives, in our analysis, we will group CHC

together according to generation (i.e., the 'second' generation containing levonorgestrel, norgestimate and norethisterone; third generation containing gestodene, desogestrel; and the newer generations containing drospirenone, norelgestromin and cyproterone acetate).

Analysis

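### The CHC generation groups hold different progestogens in the Netherlands than in Denmark and the UK, and the Danish and UK second generation leaves out norethisterone

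*Protocol*

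**What the plan says.** Three work packages in Section 9.2 define the generations, each under its Oral contraceptives heading. Each list is introduced by i.e., so it reads as a definition and not as a set of examples.

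- **WP1 (Netherlands):** "the 'second' generation containing levonorgestrel, norgestimate and norethisterone; third generation containing gestodene, desogestrel", followed by "the newer generations containing drospirenone, norelgestromin and cyproterone acetate".
- **WP2 (Denmark) and WP3 (UK), in identical wording:** "the second generation containing levonorgestrel/norgestimate and ethinylestradiol", then "the third generation containing gestodene/desogestrel and ethinylestradiol and the newer generations containing drospirenone and ethinylestradiol".

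No reason is given for the difference. All three say that the grouping comes on top of the analysis of individual products.

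WP1 gives the EMA review's risk ranking as its reason for grouping. Section 7 says that the Commission decision told prescribers "the type of CHC with the lowest VTE risk (levonorgestrel, norethisterone, or norgestimate". The risk table in the Abstract (Section 4) puts the same three progestogens in its lowest row for CHC users. It has a separate row for "Women using a CHC containing etonogestrel or norelgestromin", one row for drospirenone, gestodene and desogestrel together, and one row of products whose risk is not yet known.

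WP4 (Netherlands) and WP6 (UK) then ask whether changes in the share of each generation go with changes in VTE incidence among initiators. WP7 brings WP1 to WP6 together in one report.

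**The concern.** The study asks whether prescribing moved after the Commission decision and whether VTE incidence followed. At group level, the natural reading of uptake is the share of starters on second-generation products. If a product that the decision favours is in that group in one country and in no group in the other two, the same label measures different things. The newer generation has the same problem: it holds three progestogens in WP1 and one in WP2 and WP3. The combined report would then set the countries side by side under shared names with unlike contents. In the UK, the incomplete second-generation share would also feed the link to VTE in WP6.

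**Working it through.** No stated sample size or event count depends on this point, so there is no figure of the plan to reproduce. The check compares the lists as sets and then gives an illustration.

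**Step 1. Lists against the risk table.** Inputs: the generation lists of WP1, WP2 and WP3 in Section 9.2, and the risk table in the Abstract (VTE per 10,000 women in a year).

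| Progestogen | Risk-table row | WP1 | WP2, WP3 |
|---|---|---|---|
| Levonorgestrel | 5-7 | second | second |
| Norgestimate | 5-7 | second | second |
| Norethisterone | 5-7 | second | none |
| Etonogestrel | 6-12 | none | none |
| Norelgestromin | 6-12 | newer | none |
| Gestodene | 9-12 | third | third |
| Desogestrel | 9-12 | third | third |
| Drospirenone | 9-12 | newer | newer |
| Chlormadinone | not known | none | none |
| Dienogest | not known | none | none |
| Nomegestrol | not known | none | none |
| Cyproterone acetate | not in table | newer | none |

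From the table:

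- Between countries, the second generation differs by norethisterone and the newer generation by norelgestromin and cyproterone acetate. The third generation has the same progestogens everywhere.
- Of the 11 progestogens in the risk table, WP1 assigns 7 and leaves 4 out. WP2 and WP3 assign 5 and leave 6 out.
- The WP1 second generation equals the lowest-risk row exactly. The WP2 and WP3 second generation is that row without norethisterone.
- The 9-12 row is split between third and newer in all three countries. A change from desogestrel to drospirenone is therefore a change of generation within one risk row.
- The WP1 newer group mixes a 9-12 product, a 6-12 product and one that the table does not list.

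**Step 2. Effect on the second-generation share in Denmark and the UK.** The documents give no product shares, so every input here is an assumption. Let L be the true share of starters on the three lowest-risk progestogens and n the norethisterone share of all starters. Take L as 60% before and 70% after, a true change of +10.0 points.

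- All CHC in the denominator: measured share = L - n.
- Norethisterone also dropped from the denominator: measured share = (L - n)/(1 - n).

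| n before, after | L - n | Change | (L - n)/(1 - n) | Change |
|---|---|---|---|---|
| 2%, 2% | 58.0 to 68.0 | +10.0 | 59.2 to 69.4 | +10.2 |
| 5%, 5% | 55.0 to 65.0 | +10.0 | 57.9 to 68.4 | +10.5 |
| 10%, 10% | 50.0 to 60.0 | +10.0 | 55.6 to 66.7 | +11.1 |
| 2%, 5% | 58.0 to 65.0 | +7.0 | 59.2 to 68.4 | +9.2 |
| 5%, 10% | 55.0 to 60.0 | +5.0 | 57.9 to 66.7 | +8.8 |
| 5%, 2% | 55.0 to 68.0 | +13.0 | 57.9 to 69.4 | +11.5 |

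With an all-CHC denominator, a stable norethisterone share lowers the level by exactly that share and leaves the change intact. The change is wrong only when the share moves. Dropping norethisterone from the denominator as well adds a smaller distortion even when the share is stable.

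**The case against.** The strongest reply is that generation is a supplementary grouping. Every product is also analysed individually, and WP4 and WP6 report VTE incidence by type as well as by generation. WP5 does not use generations at all. A Danish or UK woman who starts norethisterone therefore stays visible in the product tables and the switch counts. This stands: a reader might infer that such women vanish from the study, or that its principal exposure contrast fails, and the text supports neither.

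A reader might also infer that uptake of the recommendation is misclassified in all three countries. It is not. The Dutch second generation matches the lowest-risk row, so the omission is confined to Denmark and the UK.

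Next, the analysis is a before-after comparison within each country, and WP7 reports VTE changes country by country. No pooled estimate is corrupted, and Step 2 shows that a stable omission hardly matters for the change. This also stands, but it depends on a stability that the documents do not show.

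Last, separating drospirenone from gestodene and desogestrel is a finer cut that can be summed back, and the table's rows overlap. In Denmark and the UK, third plus newer does give the 9-12 row. In the Netherlands it does not, because the newer group also holds norelgestromin and cyproterone acetate. Leaving products of unknown risk out of the generations can be defended, but the protocol does not say that this is intended.

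What remains is that grouped results under common names are planned, two of the three names have different contents by country, and product tables do not correct the grouped ones.

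**Conclusion.** The inconsistency is plain in the text and should be fixed before analysis. As written, Danish and UK norethisterone starters are missing from the second-generation share, and second- and newer-generation shares cannot be compared across countries. Third-generation and product-level shares can. The omission reaches the VTE link only in the UK, through WP6: WP4 rests on the Dutch list, and WP5 does not use generations.

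The size cannot be derived from the documents. The range of +5.0 to +13.0 around a true +10.0 rests wholly on assumed shares and shows only the direction and mechanism. A reader might be tempted to state a fixed gap in points between countries, or to say that the error rivals the shift under study. The documents give neither product shares nor an expected shift, so no such statement can be made. Nor does the inconsistency require generations to be demoted to a secondary measure.

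**What to change.** Replace the separate lists with one common progestogen list, used in every work package that groups by generation:

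- norethisterone in the lowest-risk group in all three countries;
- a stated group for each product now unassigned (etonogestrel, chlormadinone, dienogest and nomegestrol everywhere; norelgestromin and cyproterone acetate in WP2 and WP3);
- the same denominator, all CHC, in each country.

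Alongside the harmonised generations, report shares by row of the protocol's own risk table: levonorgestrel, norethisterone and norgestimate; etonogestrel and norelgestromin; drospirenone, gestodene and desogestrel; chlormadinone, dienogest and nomegestrol. Show cyproterone acetate separately, because the table does not list it.

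The cost is a shared code list and recoding of product-level data that all three countries already plan to use. The one condition is that the extraction includes the codes for non-oral CHC; if it does not, they must be added.
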